**AMENDMENT RATIONALE AND SUMMARY:**

*Editorial, administrative changes*

- Decrease accrual to 90 (section 7.2)
- Remove any mention of Rex from the protocol (will no longer be opening at that site)
- Updated contact info for co-investigators

**AMENDMENT RATIONALE AND SUMMARY:**

*Editorial, administrative changes*

- PI change from [name] to [name]

**AMENDMENT RATIONALE AND SUMMARY:**

*Editorial, administrative changes*

- Listed existing co-investigators not already identified on the protocol (cover pages)
- Page numbers updated (table of contents)
- Registration procedures updated (section 8.3)
- Updated data management (section 7.4)

*Scientific changes*

- Accrual (section 7.2)

**AMENDMENT RATIONALE AND SUMMARY:**

*Editorial, administrative changes*

- Study personnel updated (cover pages)

*Scientific changes*

- Wording of treatment planning and delivery description updated to provide additional clarification/details (section 4.3.6)
- Additional assessments for patient treatment with steroids, narcotics, anticholinergics, and systemic therapy at various time points (section 4.3.10 & section 5.1)

*Eligibility changes*

- Narrowed treatment dose and fractionation range permitted for enrollment (section 3.1.1)
- Allowance to use of MRI-based planning simulation (section 3.2.1)
- Exclusion criterion added to explicitly state exclusion of pregnant patients (section 3.2.6)

**AMENDMENT RATIONALE AND SUMMARY:**

***Eligibility changes***

- Time frame for prior RT exclusion criterion modified from within the last year to any time within the patient's life (section 3.1.2)

[figure not shown]

## **1.0 BACKGROUND AND RATIONALE**

### **1.1 Study Synopsis**

The parotids have not been historically considered an organ at risk / avoidance structure and are not routinely delineated for whole brain radiation (WBRT) planning, despite receiving incidental dose [1] using standard fields. For this reason, we evaluated patient reported xerostomia in an ongoing prospective observational trial (LCCC 1540: Prospective Evaluation of Patient Reported Xerostomia After Whole Brain Radiation). At an interim analysis of LCCC 1540 with accrual at 90% of the goal, we found a clinically-meaningful rate of xerostomia following routine WBRT. Furthermore, the incidence/severity appeared to be related to parotid dose. The goal of this follow-up study is to investigate whether parotid sparing WBRT can reduce or prevent patient reported xerostomia. The study design will principally be a prospective randomized trial where patients are randomized to receive parotid sparing WBRT vs. standard WBRT where the parotids are not avoided. We will evaluate the xerostomia scores (using the University of Michigan Xerostomia Questionnaire [2]) of patients treated in each arm. Patients who refuse randomization will be offered enrollment in an observational arm to follow their symptoms of xerostomia for secondary analysis. This will be a multi-site study, with patients also enrolling at High Point Regional Health, High Point, North Carolina, as well as possibly other sites and institutions. We anticipate a total accrual of approximately 90 patients (45 in each interventional arm) with a goal of 62 evaluable patients reaching the primary 1 month post-RT endpoint.

### **1.2 Background**

#### **1.2.1 Salivary Gland Toxicity in Head and Neck Cancer**

It is well known that radiotherapy for head and neck cancer is associated with significant and sometimes permanent dry mouth. Numerous studies have demonstrated that the degree of parotid gland exposure is related to the severity of xerostomia [2-5]. These studies have led to a national consensus guideline regarding minimization of parotid doses (e.g., mean bilateral parotid dose should be  $\leq 25$  Gy) [6]. Due to these guidelines, it is now standard to delineate the parotid glands and to use conformal treatment techniques such as intensity-modulated radiation therapy to minimize incidental irradiation to these organs in patients being treated for head and neck cancer.

#### **1.2.2 Whole Brain Radiation – Background and Quality of Life**

Whole brain radiation is commonly used for patients with multiple brain metastases. The prognosis of most patients who require whole brain radiation is poor, with many not living beyond six months [7]. Quality of life is thus of paramount importance in this population. Numerous prospective studies have reported on the well-known side effects of fatigue, alopecia, and neurocognitive decline following WBRT. This is balanced with the potential improvement in quality of life due to control of CNS disease [8-10]. While patients do occasionally complain of dry mouth following whole brain radiation, no prior studies have systematically assessed the frequency or severity of dry mouth in these patients, though one older case series did report several cases of parotitis following WBRT [11]. We believe that these symptoms are related to

incidental irradiation of the parotids, and that simple adjustments to the traditional RT fields can mitigate this toxicity.

### **1.2.3 Whole Brain Radiation – Standard Approach, Organs at Risk, and Parotid Dose**

Due to the poor prognosis for most patients receiving whole brain radiation, and because typical total doses used for whole brain radiation are in the range of 20-35 Gy (vs. 60-70 Gy for patients with head and neck cancer), the parotids have not traditionally been considered an organ at risk in patients receiving whole brain radiation. Historically, whole brain radiation fields were designed based on the anatomy as seen on planning skull radiographs, and this ‘standard approach’ has not changed in several decades. While sophisticated computer-based techniques readily enable the consideration of 3D anatomy (e.g. from CT and/or MRI) in the treatment planning process, these newer approaches have not been applied in patients receiving whole brain radiation. The accepted standard WBRT field includes roughly 5-10mm of margin inferiorly around the cribriform plate and inferior skull, as well as coverage of the entire C1 and sometimes C2 vertebral bodies. For the purposes of WBRT, no standard normal tissues are delineated for avoidance, though the lenses are often delineated at the discretion of the treating physician.

As such, the location of the parotid glands is not considered during planning for whole brain radiation, and there are presently no dose/volume limits for the parotids. For example, in patients receiving whole brain radiation on the nationwide RTOG 0933 trial using hippocampal sparing intensity-modulated radiation, only the hippocampus, eyes, and lenses were required to be delineated with set dose limits. [12] In patients receiving whole brain radiation on other protocols, such as N107C, [13] no organs at risk are required to be delineated. Thus, the risk of radiation-associated parotid injury is not appreciated.

[figure not shown]
Nonetheless, the parotids do, in fact, receive substantial radiation dose during whole brain radiation. For instance, several dosimetric studies report mean parotid doses of 10 to 20 Gy. [1, 14, 15] However, prior to LCCC 1540 there have been no studies that have reported the clinical impact of this parotid exposure. Several lines of evidence suggest that incidental parotid irradiation may cause meaningful toxicity in patients receiving whole brain radiation:

1. Gradual dose response: Though the recommended parotid “dose limit” for patients with head and neck cancer is 20-25 Gy, there is a gradual dose response, and it is recommended that parotid dose is kept as low as possible (e.g. << 20 Gy) to minimize xerostomia. Thus, mean parotid doses in the 10-20 Gy range (as is reported with whole brain radiation) may cause toxicity.
2. Acute vs. late toxicity: Parotid dose guidelines in patients with head and neck cancer are based on late (e.g.  $\geq 1$  year post-RT) toxicity. Patients generally suffer greater acute toxicities during RT, [16] or at shorter time intervals (e.g., 1-6 months) post-RT, with some recovery of salivary function at later time points. These acute toxicities are what matter most to patients receiving whole brain radiation; given their poor prognoses, few will survive long enough for later (e.g.  $\geq 1$  year post-radiation) salivary recovery.

[figure not shown]
- Higher doses per fraction and shorter overall radiation treatment times: Though parotid doses during whole brain radiation are lower than for head and neck cancer, whole brain radiation is delivered in larger doses per fraction (2.5-3.0 Gy per fraction as opposed to 1.8-2.0 Gy per fraction for head and neck cancer) and in a shorter treatment time (e.g. 2-3 weeks as opposed to 7 weeks for head and neck cancer). Higher doses per fraction and shorter treatment intervals are both associated with increased risks of toxicity.

### 1.2.5 Preliminary Results of LCCC 1540: Prospective Evaluation of Patient Reported Xerostomia After Whole Brain Radiation

These hypotheses culminated in the design of LCCC 1540. We used the validated University of Michigan Xerostomia Questionnaire [2] and a “bother score” questionnaire to assess patient-reported xerostomia after standard whole brain radiation, in which the parotid glands were not prospectively delineated. The parotids were, however, retrospectively delineated to assess impact of parotid dose on xerostomia. Like other reports, the parotid glands received mean doses of roughly 17 Gy. However, LCCC 1540 provided the first data on the actual clinical significance of this incidental exposure. In an interim analysis with accrual at 90% of the goal, xerostomia was common, sometimes severe, and often persisted to the last post-RT assessment. Further, parotid doses were strongly correlated with xerostomia, consistent with our original hypothesis. These novel data have important implications for quality of life and perhaps even nutritional status in this vulnerable patient population, and were accepted for oral presentation this year at two national conferences (ACRO 2017 and ASTRO 2017).

**Figure 1. LCCC 1540:** Change in xerostomia score (y-axis) plotted against parotid dose (x-axis) for all 41 patients reaching the 1 month post-RT primary endpoint. Parotid doses were significantly correlated with xerostomia ( $p=0.005$ ). (Parotid V20Gy: % of the bilateral parotid glands receiving at least 20 Gy).

[figure not shown]

**Figure 2. LCCC 1540:** Mean xerostomia score change (A) and bother (B) were significantly worse in patients with higher parotid dose at most time points. (Parotid V20: % of the bilateral parotid glands receiving at least 20 Gy).

These are the first data demonstrating that dry mouth is a toxicity of WBRT and have implications on field design during treatment planning.

The results of LCCC 1540 have introduced an evolving standard of care in our department. Because coverage of the brain does not appear to be compromised with the use of parotid sparing (see Figure 3, above), several physicians who are familiar with data from LCCC 1540 have already started utilizing parotid sparing WBRT fields *off trial* to attempt to reduce toxicity. Others, on the other hand, prefer to continue to use standard WBRT without parotid avoidance given the preliminary nature of the available data and the hypothetical risk of marginal failure either in the inferior brain or upper cervical vertebrae. To investigate the hypothesis that parotid sparing provides a clinical benefit in a safe manner, we will randomize patients *on trial* to receive either parotid sparing WBRT vs. standard WBRT. If our hypothesis is correct, then the severity of xerostomia will be lower in patients randomized to parotid sparing.

## **2.0 STUDY OBJECTIVES**

### **2.1 Primary Objective**

To assess whether the use of parotid sparing WBRT fields results in decreased xerostomia compared to standard WBRT fields (where the parotids are not avoided) *in randomized patients*.

### **2.2 Secondary Objectives**

Secondary objective #1: To assess whether the use of parotid sparing WBRT fields results in an increase in marginal tumor relapses in the region of the blocked parotid glands *in randomized patients*.

Secondary objective #2: To assess whether the use of parotid sparing WBRT fields results in decreased xerostomia *in all patients, including randomized patients and patients who refused randomization but consented for the observational arm*.

### **2.3 Exploratory Objectives**

[REDACTED]

### **2.4 Endpoints**

Primary endpoint: The primary endpoint will be the proportion of patients experiencing clinically significant xerostomia (defined as a  $\geq 15$  point increase in composite University of Michigan Xerostomia Questionnaire score [2]) *in randomized patients* from baseline to 1 month post-treatment.

Secondary endpoint #1: Freedom from marginal relapse, including CNS relapse in the inferior brain (defined as within 1 cm of the block edge overlying the blocked parotids), and the rate of upper cervical spine relapse (defined as relapses in the C1 or C2 vertebrae).

Secondary endpoint #2: Xerostomia (defined as a  $\geq 15$  point increase) at 1 month based on the use of standard vs. parotid sparing fields *in all patients, including randomized and non-randomized patients*.

Exploratory endpoint: [REDACTED]

[REDACTED]

Exploratory endpoint #2: [REDACTED]

[REDACTED].

## **3.0 PATIENT ELIGIBILITY**

### **3.1 Inclusion Criteria**

The subject must meet all of the following inclusion criteria to participate in this study:

**3.1.1** Patients to be treated with WBRT using 3-dimensional conformal RT in 10-15 fractions to a total dose of 30-35 Gy for any diagnosis other than elective treatment of potentially subclinical intracranial disease.

**3.1.2** No prior radiation that would have exposed the parotids to a significant (estimated  $>10$  Gy mean parotid dose) level of radiation. Patients receiving prior stereotactic radiosurgery for brain metastasis are eligible for inclusion in this trial as this form of radiation is highly conformal and exposes the parotids to minimal (estimated  $<1$  Gy) radiation.

- Patients enrolling on the observational arm may have started their current course of whole brain radiation therapy within 5 days prior to completing the baseline screening questionnaire and consenting to study.

**3.1.3** Greater than or equal to 18 years of age (no upper age limit).

**3.1.4** Raw xerostomia score  $< 40 / 80$  on the initial screening xerostomia questionnaire. This is calculated by adding up the values from questions 1-8.

**3.1.5** Initial xerostomia questionnaire and informed consent obtained within the required time frame ( $\leq 30$  days before RT start for interventional arm;  $\leq 5$  days after RT start for observational arm).

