## **3.2 Exclusion Criteria**

The subject may be excluded or withdrawn from the study if any of the following apply:

**3.2.1** Patients receiving WBRT without the use of a CT or MRI-based planning simulation.

**3.2.2** Patients receiving WBRT with the use of intensity-modulated radiation therapy.

**3.2.3** Patient receiving WBRT as elective treatment of potentially subclinical intracranial disease (e.g., WBRT for prophylactic cranial irradiation of small cell lung cancer).

[figure not shown]
**3.2.4** Physically unable to communicate by paper or phone to complete the study survey.

**3.2.5** Prisoners.

**3.2.6** Pregnant women.

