#### **4.3.5 Treatment Planning and Delivery – Arm A: Standard WBRT (Control Arm)**

Patients randomized to the control arm will receive standard WBRT without delineation or avoidance of the parotid glands, as per typical practice (see Figure 4, below). Patients must be enrolled prior to treatment. Laterally arranged beams will be designed based on digitally reconstructed skull radiographs. A 5-10 mm margin is used around the cribriform plate and skull base, with inferior extension of the field to cover the entirety of the C1 and/or C2 vertebra, with at least a 2mm margin anterior to the vertebral bodies. The parotids will *not* be delineated for avoidance, and delineation of other organs at risk or the brain is optional, consistent with most national studies utilizing WBRT (see section 1.2.3). All treatment plans are monitored for quality assurance at departmental meetings in which radiation fields are presented for peer review. Weekly X-ray films are taken to verify the accuracy of patient set up on actual treatment days. The initial treatment will not proceed without physician verification of accurate patient set up.

**Figure 4. Control arm (Standard WBRT).** Example of a laterally arranged treatment field for standard WBRT used in the control arm, where a small margin is provided around the inferior skull border. The C1 vertebra is covered with a small anterior margin. No organs at risk are standardly delineated, though providers may opt to delineate the lens and orbits for avoidance, or the brain to ensure coverage.

[figure not shown]

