#### **4.3.6 Treatment Planning and Delivery – Arm B: Parotid sparing WBRT (Intervention Arm)**

Patients randomized to the intervention arm will receive parotid sparing WBRT (see Figure 5, below). Patients must be enrolled prior to treatment.

[figure not shown]
- The left parotid will be delineated and named **Parotid\_Lt**
- The right parotid will be delineated and named **Parotid\_Rt**
- The **Parotid\_Lt** and **Parotid\_Rt** structures will be combined and named **Parotids\_Bilateral** for use in planning and dosimetric analysis.
- The **brain** will be delineated to the level of the foramen magnum, marked by the superior dens (see Figure 6, below), to ensure adequate target coverage.
- Laterally arranged beams will be designed based on both digitally reconstructed skull radiographs and CT anatomy. Radiation fields will be altered to minimize overlap with the **Parotids\_Bilateral** contour, while maintaining around a 1cm margin around the brain contour. All treatment plans are monitored for quality assurance at departmental meetings in which radiation fields are presented for peer review. Weekly X-ray films are taken to verify the accuracy of patient set up on actual treatment days.

Based on the results of the replanning analysis from LCCC 1540, 87% of patients were able to achieve a bilateral parotid V20Gy <25% while maintaining a 1cm margin around the brain, and the range of replanned bilateral parotid V20Gy was 1-35%. Thus, there will be a **goal to limit the Parotids Bilateral V20Gy to <25%, and lower if possible**. The following table summarizes the dose constraints of the parotid-sparing arm:

Parotid-sparing WBRT arm dose constraints (for Parotids Bilateral)	
Goal	V20Gy < 25%
Minor deviation	V20Gy $\geq$ 25% to < 35%
Major deviation	V20Gy $\geq$ 35%

**Figure 5. Intervention arm (Parotid sparing WBRT).** Example of a laterally arranged treatment field for parotid sparing WBRT used in the intervention arm. Cervical vertebrae are no longer considered in treatment planning. The parotids and brain must be delineated. Ensuring a 1 cm margin around the brain contour, the treatment field is altered to minimize overlap with the parotid glands.

**Figure 6. Intervention arm (Parotid sparing WBRT).** Contouring of the parotids (green, blue) and brain (red). The brain contour extends inferiorly to the most superior point of the dens of the C2 vertebra (dotted circle).

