### **4.4 Expected Risks**

Patients randomized to standard WBRT will not be subject to any risks specific to participation in this trial; these patients receive standard treatment and simply complete the study assessment at post-treatment time points. Several theoretic risks warrant mention for patients randomized to parotid sparing WBRT:

1. By delineating and minimizing dose to the parotids, the target (brain) could receive a lower dose, which could place the patient at higher risk of inferior brain relapse.
2. By omitting coverage of C1/C2, patients may develop bony metastases in this location which may be more difficult to treat with radiation in the future, given the abutment of the prior parotid sparing field.

For the following reasons, these risks are minimal:

1. The standard field arrangements of WBRT covering the upper cervical vertebrae have become standard practice with the advent of CT-based planning. Prior to CT-based planning, WBRT was delivered with an angled rectangular field splitting the cervical vertebrae. With the use of CT-based planning, WBRT fields became horizontal, and coverage of the cervical vertebrae was added to provide an additional margin around the foramen magnum. However, our preliminary analysis of LCCC 1540 and other studies [15, 18] show that coverage of brain is minimally affected with alterations to the field to maximize sparing of the parotids. Some of these studies have done this by omitting the upper cervical vertebrae and others have simply reduced the field borders in areas overlapping with the parotids. Therefore, target coverage is not expected to be compromised.
2. Regardless of any reductions in field size and the negligible impact on dose to the brain described above, whole brain radiation is essentially treatment of mostly subclinical disease in addition to areas of actual brain metastases. However, the field of radiation oncology as a whole has generally accepted that treatment of subclinical disease in the brain is not strictly necessary. This is demonstrated by the increasing use of stereotactic radiosurgery for multiple brain metastases with *no* elective brain treatment; it is generally accepted that if these patients develop new brain metastases they can be salvaged with additional stereotactic radiosurgery. Therefore, a small margin reduction with the goal of improving patient quality of life in a population with limited life expectancy should be acceptable and entail minimal excess risk.

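### Sections 3.1 and 3.2 do not bar patients with disease already known at C1 or C2 from randomization, although Arm B plans no coverage there and the C1/C2 risk argument in 4.4 does not weigh such disease

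*Combined protocol and SAP*

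**What the plan says.** **Who may be randomized.** Section 3.1.1 admits patients receiving whole brain radiation "for any diagnosis other than elective treatment of potentially subclinical intracranial disease". The other inclusion criteria concern prior parotid dose, age, baseline dry-mouth score and timing. Section 3.2 opens with "The subject may be excluded or withdrawn from the study if any of the following apply" and lists six items: no CT or MRI simulation, intensity-modulated treatment, elective treatment, inability to communicate, prisoners, and pregnancy. None mentions the cervical spine. Section 4.3.1 offers randomization to qualifying patients identified before radiation starts and adds no spine check.

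**What each arm covers.** Arm A is planned "with inferior extension of the field to cover the entirety of the C1 and/or C2 vertebra" (4.3.5). For Arm B, the caption of Figure 5, an example field, says "Cervical vertebrae are no longer considered in treatment planning" (4.3.6). The Arm B planning bullets ask for minimal overlap with the parotids "while maintaining around a 1cm margin around the brain contour". Figure 6 places the lower limit of that contour: "The brain contour extends inferiorly to the most superior point of the dens of the C2 vertebra".

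**How the risk is argued.** Section 4.4 lists the C1/C2 risk of Arm B as follows: "By omitting coverage of C1/C2, patients may develop bony metastases in this location". It answers by pointing back to its argument on brain disease, which begins from the view that "whole brain radiation is essentially treatment of mostly subclinical disease in addition to areas of actual brain metastases". It adds that marginal bony relapses should be very rare and would remain treatable.

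**The concern.** The two randomized fields differ by design at C1/C2, and the justification for that difference concerns patients who have no known disease there. The argument in 4.4 is that subclinical disease need not be treated and that a later relapse is rare and can be salvaged. A lesion already documented at C1 or C2 at entry is neither subclinical nor a later relapse, so the argument does not reach it. The eligibility criteria still let such a patient be randomized.

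The stake is patient safety in a rare case: known disease could be assigned to a field not planned to cover it, for a reason that the protocol has not weighed. A smaller matter is secondary endpoint #1. Relapse at C1 or C2 is compared between arms by log rank test (2.4, 7.3), and no rule separates progression of disease present at entry from a new relapse.

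**Working it through.** **Step 1: set the sections side by side.**

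| Question | Where | Answer |
|---|---|---|
| Does any criterion address known C1/C2 disease? | 3.1, 3.2, 4.3.1 | No |
| Is C1/C2 covered in Arm A? | 4.3.5 | Planned for C1 and/or C2, so C2 may be missed |
| Is C1/C2 covered in Arm B? | 4.3.6 bullets | No lower limit or prohibition stated; margin of about 1 cm around the brain |
| | 4.3.6 Figure 5 caption; 4.4 | Vertebrae not considered; coverage described as omitted |
| Which C1/C2 disease does 4.4 weigh? | 4.4 | Metastases that may develop later; subclinical disease; rare, treatable relapse |
| Is C1/C2 disease known at entry discussed? | 4.4 | No |

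The contrast between arms is one of planning intent, not all or nothing. Because the brain contour stops at the top of the dens, a margin of about 1 cm around it may give part of C1/C2 some incidental dose.

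**Step 2: reproduce the planned sample size (context for the cost of a fix).** Inputs from 7.2: 42% against 14%, one-sided 0.05, 80% power. With pooled proportion (0.42 + 0.14)/2 = 0.28 and no continuity correction:

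n per arm = [1.645 × √(2 × 0.28 × 0.72) + 0.842 × √(0.42 × 0.58 + 0.14 × 0.86)]² / 0.28² = 30.7, rounded up to 31.

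This matches the plan; power at 31 per arm is 80.3%. At 70% completion, 45 enrolled per arm gives 45 × 0.70 = 31.5 evaluable per arm and power of 80.9%.

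**Step 3: size of the gap.** The documents give no prevalence p of known C1/C2 disease among eligible patients. Every p below is an assumption. Formulas:

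- Expected number in Arm B = 45p.
- Chance of at least one in Arm B = 1 − (1 − p)^45.
- Patients to screen in order to randomize 90 = 90/(1 − p).
- Evaluable per arm if excluded patients are not replaced = 31.5(1 − p), entered into the power formula of Step 2.

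| Assumed p | Expected in Arm B | Chance of at least one | Screened for 90 | Evaluable per arm, not replaced | Power, not replaced |
|---|---|---|---|---|---|
| 0.1% | 0.05 | 4.4% | 90.1 | 31.47 | 80.8% |
| 0.5% | 0.23 | 20.2% | 90.5 | 31.34 | 80.7% |
| 1% | 0.45 | 36.4% | 90.9 | 31.19 | 80.5% |
| 2% | 0.90 | 59.7% | 91.8 | 30.87 | 80.2% |
| 5% | 2.25 | 90.1% | 94.7 | 29.93 | 79.0% |

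The third column runs from 4% to 90% purely because p is unknown, so it says little about the true risk. It also counts patients with known disease, not patients left untreated, so at each p it is an upper bound on harm. The last three columns are more useful: across the whole range, exclusion costs almost nothing. If excluded patients are replaced, power does not change.

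**The case against.** The strongest reply is that the treating physician keeps ample room to protect such a patient.

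- **Before randomization:** the physician can simply not offer the trial.
- **In planning:** the Arm B bullets do not prohibit covering a vertebra, the parotid V20Gy limit is a goal with graded deviations, and no central plan approval is required before treatment (4.3.8). The simulation scan includes the whole neck (4.3.4), and fields go to departmental peer review.
- **Afterwards:** separate cervical treatment is not forbidden, and 8.4 and 8.4.1 allow departures in an emergency or for an immediate hazard.

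This largely stands as a reason to expect little harm. It does not close the gap, because none of these is an eligibility rule applied before randomization. The emergency clauses act afterwards. The absence of central approval leaves the physician free to adapt the field, but it also means that the study does not check the plan first. A field widened after assignment to Arm B could also be judged incorrect treatment, which 4.3.8 removes from the primary analysis.

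A reader might infer more than the documents support:

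- *Arm B forbids covering C1/C2.* It does not. The omission is described in 4.4 and in an example caption, and the operative bullets are silent.
- *Arm A guarantees coverage.* It does not: C1 and/or C2 leaves room to miss C2.
- *All of 4.4 rests on subclinical disease and later relapse.* It also argues from preserved brain coverage and from adoption of parotid sparing elsewhere. The limitation applies to its C1/C2 argument.
- *The relapse comparison is invalid.* Randomization tends to balance baseline disease, relapse is read from routine follow-up without protocol imaging (4.3.11), and disease unknown at entry would blur the endpoint even after the fix. The gain there is minor.

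**Conclusion.** The point holds as a gap in eligibility. As written, the plan allows a patient with known C1/C2 disease to be randomized to a field not planned to cover it, and the C1/C2 argument in 4.4 does not weigh that situation. Harm is possible but unlikely, and the documents do not support saying that any patient would be left untreated.

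The size cannot be fixed from the documents. At an assumed prevalence of 1% to 5%, between 0.45 and 2.25 Arm B patients would be expected to have such disease; below 1% the expected number is under half a patient. The effect on the primary analysis is negligible. The conclusion rests on the eligibility text in 3.1 and 3.2. The eligibility checklist mentioned in 8.3 is not in the reviewed text and may already carry such a question. The change is worth considering because it costs almost nothing, not because the trial is unsound without it.

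**What to change.** Add one item to 3.2, for the randomized arms only: *Disease at C1 or C2 known from existing records at screening: not eligible for randomization.* The firm wording matters because the lead-in to 3.2 says only that a patient may be excluded. Confirm the item on the eligibility checklist at registration (8.3). Require no new imaging, and leave the Arm C entry rules as they are.

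The cost is one protocol line, one checklist line and a very small loss of randomized accrual. At an assumed 1% to 5%, about 1 to 5 more patients are screened to randomize 90 (90.9 − 90 = 0.9; 94.7 − 90 = 4.7). If they were not replaced, power would be 80.5% to 79.0%, against 80.9%.

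The alternative is a sentence in 4.3.6 allowing coverage of known C1/C2 disease in Arm B. That would protect the same patients and keep them in the trial. However, it would enlarge the field in some Arm B patients and leave the relapse definition unclear for them, so the exclusion is simpler.
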